11.4 Final Analysis Plan

The primary analysis of the primary endpoint will be performed according to an intention-to-treat (ITT) approach and include all randomized subjects. As (secondary) sensitivity analyses of the primary endpoint, complete case analyses using the CC-V1 / ATP-V1 cohorts (defined below) and a worst case analysis using the ITT cohort of the primary endpoint will be performed. Additional analyses may be performed and are described in detail in the Statistical Analysis Plan.

Intention-to-Treat Cohort: All randomized participants, analyzed as randomized. Subjects that have not received at least one dose of study product will have adequate clinical response and its sub-components treated as missing.

Complete Case Cohorts (CC): Subjects in a CC analysis are analyzed as randomized, but excluded from analysis if missing data prevents assigning an unambiguous value to the DOOR endpoint or if the subject has not received at least one dose of study product. The CC-V1 cohort will consist of all subjects with sufficient data to define unambiguously the Visit #1 DOOR. The CC-V2 cohort will consist of all subjects with sufficient data to define unambiguously the Visit #2 DOOR.

According-to-Protocol Cohorts (ATP): Subjects in an ATP analysis require at least one dose of study product each day from Day 1 to Day 5 and furthermore subjects will be excluded from analysis if missing data prevents assigning an unambiguous value to the DOOR endpoint. The ATP-V1 cohort will restrict subjects to those with sufficient data to define unambiguously the Visit #1 DOOR. The ATP-V2 cohort will restrict subjects to those with sufficient data to define unambiguously the Visit #2 DOOR.

Details of what constitutes sufficient data to assign an unambiguous value to DOOR will be specified in the statistical analysis plan.

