- Separately for Outcome Assessment Visit #1 and #2, using CC cohorts, a forest plot of 95% confidence intervals for the risk difference of adequate clinical response as well as the following interventions for persistent or worsening pneumonia: (1) ED/clinic visits, (2) hospitalizations, (3) surgical procedures, and (4) non-study systemic antibiotics. Tests for differences in proportions between treatment arms will be given by Fisher's exact tests.
 - Separately for Outcome Assessment Visit #1 and #2, using CC cohorts, a forest plot of 95% confidence intervals for the risk difference of adequate clinical response as well as the following interventions for all causes: (1) ED/clinic visits, (2) hospitalizations, (3) surgical procedures, and (4) non-study systemic antibiotics. Tests for differences in proportions between treatment arms will be given by Fisher's exact tests.
 - Analysis of the ordinal clinical response at Outcome Assessment Visits #1 and #2. The ITT analysis will treat the ordinal clinical response as Normal distributed and use multiple imputation to compute confidence intervals for the mean ordinal clinical response by treatment assignment and to test whether the mean ordinal clinical response varies by treatment assignment. CC, ATP, and worst case analyses of the ordinal clinical response will be performed; separately for Outcome Assessment Visit #1 and #2, a cumulative difference plot with respective 95% confidence bands for the ordinal clinical response (and an associated result from a Mantel-Hantzel chi-square test on the ordinal clinical response) will be computed. Non-inferiority analyses of the ordinal clinical response at Outcome Assessment Visits #1 and #2 using the ITT cohort, to be specified in the statistical analysis plan, may be carried out.

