Randomization: Enrolled subjects will be randomized to short vs. standard course therapy at a 1:1 ratio, with stratification by 1) age group (<24 months vs. 24-71 months), 2) initially prescribed antibiotic (amoxicillin vs. amoxicillin-clavulanate vs. cefdinir), and 3) treatment site (emergency department vs. outpatient clinic/urgent care facility).

Intervention: Subjects will continue on the initially prescribed antibiotic through Day -1, until they have completed 5 days (i.e., 5 scheduled doses of once daily medication, 10 scheduled doses of twice daily medication) of antibiotic therapy [e.g., if a subject takes the first dose of antibiotic in the afternoon of Day -5, the first dose of study agent would occur on the afternoon of Day 1, providing 10 total scheduled doses of a twice daily prescribed antimicrobial]. The first day of receipt of study agent will be Day 1. Subjects assigned to standard course therapy will receive 5 additional days (10 doses) of the same initially prescribed antibiotic, with standardized twice-daily dosing. Subjects assigned to short course therapy will receive 5 more days (10 doses) of a matching placebo. Both the study agent and placebo may appear different than the commercial formulation the child originally received. The placebo will appear indistinguishable in color, taste, thickness, and consistency from the active antibiotic the child would otherwise

receive in the study. The study product will be labeled with a numerical code that masks site investigators, site staff, parent(s)/guardian(s) and children to the formulation.

Follow-up and Assessment of Endpoints: Subjects will be scheduled for the following assessment visits:

[figure not shown]
Visit 2: Outcome Assessment Visit #1, Day 6 to 10 (1-5 days after completing the study agent). Subjects will be evaluated for the components of the composite overall outcome, which include the adequacy of the subject's clinical response; persistence of symptoms of fever, tachypnea, or cough; the occurrence of any solicited events; and the duration of antibiotic therapy (both study product/placebo and any additional oral or parenteral antibiotic therapy prescribed by study or non-study providers).

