6.4. Covariates and Subgroups

Subjects will be recruited from multiple clinical sites, but randomization will not be stratified by site. Randomization will use a total of 12 strata, with stratification by 1) age group (<24 months vs. 24-71 months), 2) initially prescribed antibiotic (amoxicillin vs. amoxicillin-clavulanate vs. cefdinir), and 3) treatment site (emergency department vs. outpatient clinic/urgent care facility).

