8.1.1. Primary Analysis of DOOR at Outcome Assessment Visit #1

DOOR at Outcome Assessment Visit #1 is defined in Section 3.3.

The null hypothesis corresponding to the primary analysis of this study is:

H0: The sum of the probability that a subject assigned to the 5-day arm will have a higher DOOR at Outcome Assessment Visit #1 than if assigned to the 10-day arm plus one-half the probability of equal DOORs at Outcome Assessment Visit #1 is 50% (i.e., no difference in DOOR at Outcome Assessment Visit #1).

The above null hypothesis can be tested using a Mann-Whitney U Test (Evans 2015).

The primary analysis will use multiple imputation with a linear model to impute missing DOOR at Outcome Assessment Visit #1 outcomes. Details of multiple imputation methods are described in Section 8.4.1.

For each of the 20 complete multiply imputed datasets, a Mann-Whitney U statistic will be computed using randomization to short course versus randomization to standard course to define the binary grouping and DOOR at Outcome Assessment Visit #1 as the outcome. The U statistics are asymptotically normal distributed, and so they can be combined into a single test statistic using Rubin's Rules (Marshall 2009).

Defining the following:

n_1 : number of subjects in ITT cohort randomized to a short course of antibiotics

n_2 : number of subjects in ITT cohort randomized to a standard course of antibiotics

m : number of imputed datasets ($m = 20$)

Q_i : U statistic computed from the i^{th} multiply imputed dataset

$$\bar{Q} = \frac{1}{m} \sum_{i=1}^m Q_i$$

Q_0 : the expected value of a U statistic under the null hypothesis ($Q_0 = \frac{n_1 n_2}{2}$)

\bar{U} : The within imputation variance (this is not the mean of the U statistics). Correcting for ties, the formula for the within imputation variance of U is:

$$\bar{U} = \text{Var}(Q_i) = \frac{n_1 n_2}{12} \left[(n_1 + n_2 + 1) - \sum_{c=1}^D (M_c^3 - M_c) \right] \quad (\text{Lehmann 1975, Zhao 2008}),$$

where M_c is the number of tied ranks for the c^{th} value DOOR in the dataset and D is the number of distinct values of DOOR in the dataset. Because the numbers of tied ranks should be very similar across the 20 multiply imputed datasets, the number of ties will be counted from the first imputed dataset only, and those counts will be used to compute the corrected variance.

$$B = \frac{1}{m-1} \sum_{i=1}^m (Q_i - \bar{Q})^2$$

$$T = \bar{U} + \frac{m+1}{m} B$$

$$W = \frac{(\bar{Q} - Q_0)^2}{T}$$

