8.2.6.1. ITT Analyses of OCR at Outcomes Assessment Visit #1

Twenty (20) multiple imputation datasets for OCR at Outcome Assessment Visit #1 will be generated in manner analogous to that described in Section 8.1.1, except using OCR at Outcome Assessment Visit #1 in place of DOOR at Outcome Assessment Visit #1 for the response. Also, analogous to Section 8.1.1, the Mann-Whitney U statistic will be computed for each of the datasets and combined using Rubin’s Rules to generate the test statistic W and a p-value for the test of the null hypothesis that

$$\Pr(\text{OCR at Outcome Assessment Visit \#1 is better in short course}) + 0.5 \Pr(\text{OCR at Outcome Assessment Visit \#1 is equal}) = 0.5.$$

The F-test using the W statistic will be inverted to produce a 95% confidence interval for $\Pr(\text{OCR is better in short course}) + 0.5 \Pr(\text{OCR is equal})$. Whether the lower bound of this confidence interval is greater than 0.4 will serve as a test of the non-inferiority null hypothesis that

$$\Pr(\text{OCR at Outcome Assessment Visit \#1 is better in short course}) + 0.5 \Pr(\text{OCR at Outcome Assessment Visit \#1 is equal}) < 0.40.$$

Results will be reported in [Table 30](#).

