8.2.6.2. ITT Analyses of OCR at Outcomes Assessment Visit #2

Twenty (20) multiple imputation datasets for OCR at Outcome Assessment Visit #2 will be generated in manner analogous to that described in 8.2.1, except using OCR at Outcome Assessment Visit #2 in place of DOOR at Outcome Assessment Visit #2 for the response. Also, analogous to 8.2.1, the Mann-Whitney U statistic will be computed for each of the datasets and combined using Rubin’s Rules to generate the test statistic W and a p-value for the test of the null hypothesis that

$$\Pr(\text{OCR at Outcome Assessment Visit \#2 is better in short course}) + 0.5 \Pr(\text{OCR at Outcome Assessment Visit \#2 is equal}) = 0.5.$$

The F-test using the W statistic will be inverted to produce a 95% confidence interval for $\Pr(\text{OCR is better in short course}) + 0.5 \Pr(\text{OCR is equal})$. Whether the lower bound of this confidence interval is greater than 0.4 will serve as a test of the non-inferiority null hypothesis that

$$\Pr(\text{OCR at Outcome Assessment Visit \#2 is better in short course}) + 0.5 \Pr(\text{OCR at Outcome Assessment Visit \#2 is equal}) < 0.40.$$

Results will be reported in [Table 31](#).

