8.3.2. Stratified (ITT) Analyses of DOOR at Outcome Assessment Visit #1

Analysis of DOOR at Outcome Assessment Visit #1 as described in Section 8.1.1 will be performed separately for each level of each stratification variable (e.g. an analysis of all subjects of age <24 months at enrollment, and a separate analysis of all subjects of age 24-71 months at enrollment) and by clinical site. Results will be reported [Table 47](#).

8.3.3. As Treated Analysis of Effect of Number of Days of Antibiotic Use on OCR at Outcome Assessment Visit #1 and Outcome Assessment Visit #2

The analysis will be performed using the subset of the CC-V1 analysis population that did not receive off-study systemic antibiotic unrelated to pneumonia prior to Outcome Assessment Visit #1. The justification for excluding subjects with unrelated antibiotic use is that subjects receiving unrelated antibiotics are at risk for both improved outcomes due to ongoing antibiotic use as well as increased side effects related to antibiotics administration. The effect of the number of days of antibiotic use at Outcome Assessment Visit #1 on OCR at Outcome Assessment Visit #1 will be analyzed using a proportional odds model that simultaneously uses all cumulative logits (Agresti 2003).

Let \mathbf{K} be the set of distinct OCR values observed at Outcome Assessment Visit #1, with the exception that the highest (worst) distinct value observed is not included in the set.

Let Y_i = the OCR of subject i at Outcome Assessment Visit #1.

Let X_i = the number of days of antibiotic use at Outcome Assessment Visit #1 for subject i .

α_k , where $k \in \mathbf{K}$, and β are parameters to be simultaneously estimated through maximum likelihood methods.

Then, proportional odds model with cumulative logits is defined as

$$\text{Logit } [P(Y_i > k)] = \alpha_k + \beta X_i, \quad k \in \mathbf{K}$$

The following gives the interpretation of the model. Suppose D is any non-negative integer.

$$\text{Then, } \log[\text{odds}(\text{OCR} > k \mid X_i = D+1) / \text{odds}(\text{OCR} > k \mid X_i = D)] = \beta.$$

That is, for any k , where k is from the set of observed OCR values at Outcome Assessment Visit #1 besides the highest observed value, e^β gives the odds ratio of an OCR at Outcome Assessment Visit #1 greater than k for the effect of one additional day of use of antibiotic.

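### Randomisation is stratified by three factors, but no planned DOOR or OCR analysis adjusts for or pools over them: a minor efficiency point, mainly for OCR non-inferiority

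*SAP*

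**What the plan says.** SAP 4.1 states: "Enrolled subjects will be randomized to short vs. standard course therapy at a 1:1 ratio, with stratification by 1) age group", followed by initial antibiotic and treatment setting. SAP 6.4 adds: "Randomization will use a total of 12 strata".

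The analyses do not use these factors to compare the arms:

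- **DOOR (SAP 8.1.1, 8.2.1).** In each imputed dataset, "a Mann-Whitney U statistic will be computed using randomization to short course versus randomization to standard course to define the binary grouping". The results are combined by Rubin's rules. The complete-case, according-to-protocol and worst-case analyses in 8.2.2 use the same unstratified U.
- **OCR (SAP 8.2.6.1, 8.2.6.2).** The same U is used for superiority and for non-inferiority: "Whether the lower bound of this confidence interval is greater than 0.4 will serve as a test of the non-inferiority null hypothesis". Visit 2 repeats this, "except using OCR at Outcome Assessment Visit #2 in place of DOOR at Outcome Assessment Visit #2 for the response".
- **SAP 8.3.2.** The heading calls these analyses stratified, but the DOOR analysis "will be performed separately for each level of each stratification variable", and by site, with no pooled result.
- **Elsewhere.** The strata are covariates in the imputation model (SAP 6.5, 8.4.1) and define the interim forest plots (SAP 6.6). SAP 10 lists nothing further.

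The protocol leaves room for more. Section 11.4.2 says OCR non-inferiority analyses "using the ITT cohort, to be specified in the statistical analysis plan, may be carried out", and section 11.4 says: "Additional analyses may be performed and are described in detail in the Statistical Analysis Plan".

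**The concern.** When allocation is balanced on factors that predict outcome, a test that ignores them keeps between-stratum variation in its standard error. The test then tends to be slightly conservative, and its confidence interval is wider than it needs to be. The SAP gives no reason for leaving the factors out of the comparison.

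The question matters most for OCR non-inferiority. In DOOR, equal clinical outcomes are separated by antibiotic days, which favours the short course and pushes power up. OCR has no such tie-break. It addresses the risk named in Protocol 2.3.1, that children treated for less time may respond less well. Precision counts there if the true index lies a little below 0.50.

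**Working it through.** The index is Pr(short course better) + 0.5 Pr(equal).

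**1. The plan's own figure.** The SAP 5 formula with c = 0.5 gives N = (1.960 + 1.282)² / [3(p − 0.5)²], which is 351, 156 and 88 at p = 0.60, 0.65 and 0.70. The SAP states 360, 160 and 90, and 360/0.90 = 400. The sample size reproduces.

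**2. Primary DOOR test, analytic.** Inputs from the documents: 180 per arm, two-sided 0.05, index 0.60. Assumed: the strata explain a share R² of rank variance between 0 and 0.10. Ties are ignored here.

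- s0 = √[(N+1)/(12·n1·n2)] = √[361/(12·180·180)] = 0.0305, and d = 0.10.
- Adjusted power = Φ(d/(s0√(1−R²)) − 1.96): 90.7% at R² = 0 and 93.3% at R² = 0.10.
- Planned power if allocation is blocked = Φ((d/s0 − 1.96)/√(1−R²)): 90.7% and 91.8%. The gain is 0 to 1.5 points.
- Planned power if not blocked = Φ(d/s0 − 1.96) = 90.7%. The gain is 0 to 2.6 points.
- Planned type I error if blocked = 2Φ(−1.96/√(1−R²)): 5.0% falling to 3.9%. If not blocked it stays at 5%.

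If OCR is equal between arms, adherence is full and half the children have OCR = 1 (assumed), the DOOR index is at least 0.5 + 0.5[0.25 + 7(0.5/7)²] = 0.643. There the gain is at most 0.06 points (blocked) or 0.17 (not blocked). Three other assumed OCR distributions put the index at about 0.61 to 0.66.

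**3. OCR non-inferiority, simulated.** Assumed inputs: N = 360; 45% under 24 months; 40% ED; antibiotics 80/10/10%; OCR levels 1–7 at 50/22/8/2/13/4/1%; blocks of 4 within 12 strata, or simple 1:1; standard tie correction; 10,000 trials per cell. An R² of 0.10 corresponds to gaps of 27 points (age) and 13 points (setting) in the share with OCR = 1. Gains in power, in percentage points:

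| True index | Allocation | R² 0 | 0.02 | 0.05 | 0.10 |
|---|---|---|---|---|---|
| 0.50 (planned about 94–95%) | blocked | −0.1 | 0.2 | 0.5 | 0.8 |
| 0.50 | simple | −0.3 | 0.0 | 0.5 | 1.2 |
| 0.46 (planned about 55%) | blocked | −0.1 | 0.8 | 1.9 | 4.0 |
| 0.46 | simple | −0.8 | 0.2 | 1.3 | 4.4 |

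The Monte Carlo error of these gains is 0.05 to 0.33 points. Separate simulations with strongly prognostic strata gave gains of 1.0 to 1.8 points at 0.50. At 0.46 they gave mostly 4 to 5, with one unblocked result of 2.7 (55.2% to 57.9%). With multiple imputation at N = 400 and R² of 0.10, the gains were 1.0 and 3.7.

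**4. Is adjustment safe for OCR?** With a true index at the 0.40 margin, false non-inferiority was 2.0–2.7% for the planned test and 2.3–2.8% adjusted, against a nominal 2.5%. A heteroscedasticity-robust standard error kept nearly all of the gain (59.3% power, against 59.9% with the ordinary one).

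**5. Is it safe for DOOR?** Less so. At an index of about 0.66, the adjusted 95% interval covered 93.1–93.3% with the ordinary standard error and 93.3–93.5% with a sandwich one. The planned interval covered 94.2–95.4%. At an interim N of 120, null rejection at p < 0.001 was 0.12–0.14% adjusted and 0.05–0.10% planned.

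**6. Would a 12-stratum van Elteren test do?** It gave no gain for OCR non-inferiority (94.5% to 94.4%, and 95.6% to 95.1%). It also targets a within-stratum probability, for which the 0.40 margin was not set. Under the assumed shares the smallest stratum holds 0.45 × 0.10 × 0.40 × 400, or about 7 children, and about 2 at N = 120.

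**The case against.** The strongest reply is that nothing here is broken. Protocol 11.4.1 and SAP 8.1.1 agree on one unadjusted test, the sample size was built for it, and U/(n1·n2) estimates exactly the probability in the hypothesis. The strata already enter the imputation, and SAP 8.3.2 would show heterogeneity across levels. The size of the gain rests entirely on assumed inputs. The largest figure needs both strongly prognostic strata and a true index of 0.46, a value the documents never use. It concerns one secondary test that the protocol treats as optional.

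Most of this stands, and it is why the point is minor and the planned primary test should stay. It does not remove the suggestion. The factors are already collected, a pooled OCR analysis costs little, and the level-by-level results in 8.3.2 cover only DOOR at Visit 1 and are never combined.

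A reader might go further and infer that omitting the strata invalidates the primary test, or leaves it underpowered. The documents do not support that: type I error is at or below 5% and power is about 90.7% or more at the design index of 0.60. Nor do they support making the adjusted analysis primary, since its regression interval covers too little for DOOR away from 0.50.

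**Conclusion.** The point holds as a minor efficiency matter. It is certain that no planned DOOR or OCR analysis adjusts for or pools over the stratification factors. The size of the benefit is not certain, because prognostic strength, blocking and the OCR distribution are not given.

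For OCR non-inferiority, the change in power runs from a loss of up to about 0.8 points, if the strata predict nothing, to a gain at an assumed R² of 0.10 of about 1 to 2 points at index 0.50 and about 4 to 5 at 0.46. For the primary DOOR test it is at most 1.5 points (blocked) or 2.6 (not blocked) at index 0.60, and under 0.2 at 0.643.

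The statement that the planned test is valid assumes the standard tie correction. The tie formula printed in SAP 8.1.1 is a separate question and matters more than this one.

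**What to change.** Before any unblinding, add a strata-adjusted OCR analysis to SAP 8.2.6.1 and 8.2.6.2:

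- Within each imputed dataset, rank OCR with 1 as best. Regress the ranks on arm (1 = short course), age group, setting and initial antibiotic, as main effects.
- Take the index as 0.5 minus the arm coefficient divided by N, with a named heteroscedasticity-robust standard error.
- Combine the index and its squared standard error by Rubin's rules.
- Report U/(n1·n2) beside it, and state in advance which of the two lower bounds decides non-inferiority at 0.40.

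Keep the planned unadjusted Mann-Whitney test as the primary and interim DOOR analysis. For DOOR (8.1.1, 8.2.1), add the adjusted index only as a prespecified sensitivity analysis. Take its standard error or interval from a bootstrap within arm (and stratum factors), because the ordinary and sandwich regression standard errors are too small away from 0.50. If data by arm have already been seen, label every adjusted result as sensitivity.

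The cost is SAP text and a little programming, an index slightly less direct to explain, and a possible loss of under 1 point of power if the strata are not prognostic. No new data are needed, and no protocol amendment, because the primary analysis does not change.
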